6.4 STUDY INTERVENTION COMPLIANCE

Two important goals of this protocol are to optimize adherence to the pharmacological regimen and to maximize the retention of participants in the study. Assessment of adherence to the assigned study drug will provide clinic staff a means to identify participants having problems with adherence. Adherence will be assessed during the trial by conducting a brief, structured interview, in which the study coordinator will assist the patients in identifying problems in taking the study drug and in estimating adherence to the prescribed medicine since their previous visit. These assessments will guide the consideration of strategies to improve adherence. Resources may be provided by clinics to remove barriers to participation such as child care,

transportation, and parking expenses. These resources can be provided as cash, transportation vouchers, or parking passes. An honorarium may be paid to participants in recognition of their time and effort when scheduled visits and procedures are completed successfully. Certificates of appreciation may be given at randomization and at conclusion of the VEDS trial as an incentive. Counts of capsules in the patient's returned blister packaging will be used as a measure of adherence at the end of the treatment period.

6.5 CONCOMITANT THERAPY

For this protocol, a prescription medication is defined as a medication that can be prescribed only by a properly authorized/licensed clinician. Medications to be reported in the Case Report Form (CRF) are concomitant prescription medications, over-the-counter medications, and supplements.

6.5.1 RESCUE MEDICINE

N/A

7 STUDY INTERVENTION DISCONTINUATION AND PARTICIPANT DISCONTINUATION/WITHDRAWAL

7.1 DISCONTINUATION OF STUDY INTERVENTION

If the participant is in the treatment phase of the trial, and he/she develops a treatment related CTCAE v5.0-defined adverse event grade 3 or above, the medication will be stopped and the participant assessed by the site study investigator who is a licensed physician/hepatologist. If the adverse event was severe, prolonged, or in the view of the investigator the participant is intolerant of the medication, the study drug will be stopped and the participant will no longer receive the study medication, but will continue to be followed in the study according to the protocol, in keeping with the "intention-to-treat" paradigm.

Participants will be monitored for drug induced liver injury and will use the scale below to grade the adverse effects*:

	Grade 1	Grade 2	Grade 3	Grade 4
ALT	BSL elevated: 3x BSL or >400 U/L	BSL elevated: >3-5x BSL	BSL elevated: >5 -20x BSL	BSL elevated: >20x BSL
AST	BSL nl:3 x ULN BSL elevated: 3x BSL	BSL nl:>3-5 x ULN BSL elevated: >3-5x BSL	BSL nl:>5-20 x ULN BSL elevated: >5-20x BSL	BSL nl:>20 x ULN BSL elevated: >20x BSL
Total Bilirubin	1.5 x ULN	>1.5-3.0 x ULN	>3.0-10.0 x ULN	>10.0 x ULN

Any participant found to meet the above criteria for grade 2 or higher drug induced liver injury will have the study medication stopped pending further study investigator evaluation.

In addition, participants will have the study medication stopped if **ANY** of the following occur[81]:

If normal baseline AST:

- AST value $>5 \times \text{ULN}$ in two repeat tests (within 14 days); OR
- AST value is $>8 \times \text{ULN}$; **OR**
- AST value $>5 \times \text{ULN}$ AND total bilirubin $>2 \times \text{ULN}^\ddagger$ OR presence of symptoms suggesting liver injury (severe fatigue, nausea, vomiting or right upper quadrant pain),

If elevated baseline AST or ALT:

- ALT or AST value $>3 \times \text{BSL}$ or 300 U/L in two repeat tests (within 14 days); OR
- ALT or AST value $>5 \times \text{BSL}$ or $>500 \text{ U/L}$ (whichever occurs first); OR
- ALT or AST value $>3 \times \text{BSL}$ or $>300 \text{ U/L}$ (whichever occurs first) AND total bilirubin $>2 \times \text{ULN}^\ddagger$ OR presence of symptoms suggesting liver injury (severe fatigue, nausea, vomiting, or right upper quadrant pain)

Follow-up visits will continue, but the study medication will not be restarted. The participant will be included in intention-to-treat analyses.

Additionally, if a participant is found to have signs of increased bleeding (i.e. petechiae) on physician assessment or a participant reports any signs of increased bleeding (i.e. bleeding gums), the study medication will be discontinued until the participant can be further examined by a study physician. The study medication may be restarted after further examination if the bleeding was not associated with a serious adverse event (CTCAE grade 3 or higher) and if the study physician deems a re-challenge appropriate.

* Values for ULN are defined at each clinical center per laboratory guidelines.

‡ For participants with suspected Gilbert's Syndrome at baseline: doubling of direct bilirubin

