5 STUDY POPULATION

5.1 INCLUSION CRITERIA

Patients must satisfy all of the following criteria to be eligible for randomization:

- 18 years of age or older as of the initial screening interview and provision of consent
- FibroScan CAP > 280 dB/m within 60 days prior to randomization.
- ALT \geq 60 U/L within 30 days of randomization

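### Section 7.1 puts a participant with normal baseline AST and elevated baseline ALT under two stopping lists, one of which can never take effect, and can stop drug permanently below the AST level that triggers only a temporary hold

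*Combined protocol and SAP*

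**What the plan says.** Section 5.1 admits participants with ALT of at least "60 U/L within 30 days of randomization". It sets no AST requirement.

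Section 7.1 then has two layers of liver rules.

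- **Grading table.** AST has separate entries for a normal baseline (multiples of ULN) and an elevated baseline (multiples of BSL, read here as the participant's baseline value). ALT has only an elevated-baseline entry. For a normal baseline AST, Grade 2 is above 3 and up to 5 times ULN. A participant at "grade 2 or higher drug induced liver injury will have the study medication stopped pending further study investigator evaluation".
- **Stopping lists.** These are introduced by "In addition, participants will have the study medication stopped if", followed by a statement that any one criterion is enough. The list headed "If normal baseline AST" stops drug at AST above 5 times ULN in two repeat tests within 14 days, or above 8 times ULN once. The list headed "If elevated baseline AST or ALT" applies to either enzyme. It stops drug above 3 times BSL or 300 U/L in two repeat tests, or above 5 times BSL or 500 U/L once. Each list also has a criterion that combines its lower multiple with bilirubin or symptoms.

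The sentence directly after the lists reads "Follow-up visits will continue, but the study medication will not be restarted". ULN is set by each center, and no value is printed.

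**The concern.** The two headings look like alternatives, but they are not mutually exclusive. The first depends on AST alone, whereas the second is met if either enzyme is elevated. Because the trial selects on raised ALT, a participant with normal AST satisfies both. The printed text then gives two different AST cut-offs for the same person, and the grading table gives a third level with a milder action.

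What is at stake is uniform safety conduct at nine centers. An irreversible action could be taken at one site and not at another on the same AST results. Section 6.3 also uses the Section 7.1 liver-injury criteria to define hepatotoxicity for the study, and Section 10.1.6 has the DSMB review incident hepatotoxicities quarterly by masked treatment group. The ambiguity can therefore reach a monitored safety count.

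**Working it through.** The plan states no figure to reproduce. The check puts the AST levels on one scale.

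**Inputs.** From Section 7.1: list 1, 5 x ULN (repeat) and 8 x ULN (single); list 2, 3 x BSL or 300 U/L (repeat) and 5 x BSL or 500 U/L (single); table hold for normal baseline AST, above 3 x ULN. From Section 5.1: ALT of at least 60 U/L. Assumed, because no ULN is printed: AST ULN of 35, 40 or 50 U/L for illustration.

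**Step 1: who meets both headings.** If the site's ALT ULN is 59 U/L or lower, 60 U/L is above it and every entrant has elevated baseline ALT. At a ULN of 60 U/L or more this is not guaranteed. The table's ALT row, which has no normal-baseline entry, is drafted as if ALT is always elevated.

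**Step 2: which list acts first.** Normal baseline AST means BSL <= ULN. Then:

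- Repeat test: 3 x BSL <= 3 x ULN < 5 x ULN.
- Single test: 5 x BSL <= 5 x ULN < 8 x ULN.
- Bilirubin or symptoms: the enzyme part is 3 x BSL in list 2 and 5 x ULN in list 1, so the first inequality applies again. The bilirubin and symptom parts are the same in both lists.

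The 300 and 500 U/L limits can only make list 2 act sooner. Any AST result that meets list 1 has therefore already met list 2. A numerical check of the repeat and single criteria over ULN 20 to 80, BSL 5 to ULN and AST 1 to 1,499 U/L (4,206,194 combinations) found no exception.

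**Step 3: permanent stop against temporary hold.** The hold starts above 3 x ULN.

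- List 2, repeat test: 3 x BSL < 3 x ULN whenever BSL < ULN.
- List 2, single test: 5 x BSL < 3 x ULN whenever BSL < 0.6 x ULN.

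**Step 4: numbers (U/L, assumed ULN and baseline).**

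| ULN | Baseline AST | List 2 repeat / single | Table hold | List 1 repeat / single |
|---|---|---|---|---|
| 40 | 20 | >60 / >100 | >120 | >200 / >320 |
| 40 | 25 | >75 / >125 | >120 | >200 / >320 |
| 40 | 30 | >90 / >150 | >120 | >200 / >320 |
| 40 | 40 | >120 / >200 | >120 | >200 / >320 |
| 35 | 25 | >75 / >125 | >105 | >175 / >280 |
| 50 | 25 | >75 / >125 | >150 | >250 / >400 |

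At ULN 40 and baseline 25, the repeat-test cut-offs differ by 200/75 = 2.7-fold.

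**Step 5: what two sites would do in that example.** The first site reads both lists literally. The second treats the headings as alternatives and takes the normal-AST list. Bilirubin is unchanged and there are no symptoms.

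- Confirmed AST of 76 to 120: the first site stops permanently and the second takes no action on AST.
- Confirmed AST of 121 to 200: the first stops permanently and the second holds pending evaluation.
- Confirmed AST above 200: both stop permanently.

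**The case against.** The best defense is that the two lists sit under one instruction, and any single criterion is enough to stop drug. Two sufficient conditions joined in this way cannot give opposite orders: the stricter one governs and the other is redundant. Followed literally, the text leads to the earlier stop, and investigators and the DSMB review abnormal results in any case. This stands as logic, so the lists should not be called contradictory. It does not explain why a list with its own heading and cut-offs was written if it can never act, or why the permanent stop can come before the temporary hold. A site that takes the headings as alternatives is making an understandable reading.

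A reader might infer more than the documents support:

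- **That drug can be stopped at an AST which the table does not grade.** The Grade 1 entry for a normal baseline is printed as 3 x ULN, and Grade 2 begins just above that. The bilirubin row has the same pattern. Grade 1 is most naturally an upper bound, so such values would usually be Grade 1. Only the comparison with the Grade 2 hold is safe.
- **That every participant falls under the second list.** This depends on local ALT limits, which are not given. The ALT normalization endpoint in Section 3 is itself restricted to participants above ULN at baseline.
- **That early stops dilute the 24-week ITT comparison.** The documents give neither the share with normal baseline AST nor a rate of AST tripling. The rule is the same in all arms and is applied under masking. No size can be put on this effect, and the point does not rest on it.

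**Conclusion.** The point holds as an internal inconsistency in Section 7.1 for participants with normal baseline AST and elevated baseline ALT. Two results follow from the printed rules for any AST ULN. The normal-AST list has no effect for these participants. Whenever baseline AST is below ULN, a confirmed AST can end treatment permanently below the level at which the table only holds drug for evaluation.

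The conclusion assumes an ALT ULN below 60 U/L at the site if it is to cover all entrants with normal AST. It also assumes that the no-restart sentence governs the lists it follows and not the table's hold, which is described as pending evaluation. The figures of 75, 120 and 200 U/L are illustrations for an assumed ULN of 40 and baseline AST of 25. The number of participants affected cannot be derived from the documents.

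**What to change.** The sponsor should reconcile the two list headings and the grading table in Section 7.1 so that:

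1. one unambiguous AST rule applies to a participant with normal baseline AST and elevated baseline ALT; and
2. the levels for a temporary hold and for a permanent stop are consistent with each other.

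Which rule and which cut-offs apply is for the sponsor's hepatology and safety leads to decide. This review proposes neither. The hepatotoxicity definition in Section 6.3 should then point to the reconciled criteria, and the rule should be programmed as a flag in the data system so that all centers apply it in the same way.

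The cost is a protocol wording change with its usual approvals and one edit check. No new tests or visits are needed.

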 - Evidence of recent or current hepatitis C as marked by the presence of anti HCV antibody with detectable HCV RNA in serum within 1 year prior to enrollment. Participants with anti HCV antibody positivity who have undetectable HCV RNA at least 1 year prior to enrollment (either due to spontaneous clearance or clearance with treatment) will be eligible to participate if HCV RNA at entry remains undetected
 - Evidence of ongoing autoimmune liver disease as defined by compatible liver histology
 - Primary biliary cirrhosis as defined by the presence of at least 2 of these criteria
 - (i) Biochemical evidence of cholestasis based mainly on alkaline phosphatase elevation
 - (ii) Presence of anti-mitochondrial antibody (AMA)
 - (iii) Histologic evidence of nonsuppurative destructive cholangitis and destruction of interlobular bile ducts[1]
 - Primary sclerosing cholangitis
 - Known history of Wilson disease, alpha-1-antitrypsin liver disease, or hemochromatosis. Any other type of liver disease that is currently active other than NASH such as drug-induced liver disease, liver cancer, or bile duct obstruction.
- Serum alanine aminotransferase (ALT) greater than 400 U/L within 90 days of randomization
- Moderate or severe renal impairment (serum creatinine ≥ 2.0 mg/dL or eGFR < 60 mL/1.73m²)
- History of biliary diversion or evidence of current biliary obstruction
- Known positivity for Human Immunodeficiency Virus (HIV) infection
- Active, serious medical disease with likely life expectancy less than 5 years
- Active substance abuse including inhaled or injection drugs in the year prior to screening
- Pregnancy, planned pregnancy, potential for pregnancy and unwillingness to use ≥ 1 effective form(s) of birth control during the trial, breast feeding
- Current use of medications that may impact the absorption of fat-soluble vitamins (i.e. orlistat or cholestyramine)
- Pre-existing history of fat malabsorption
- Males at high risk of prostate cancer, including:
 - PSA >ULN at baseline
 - History of prostate cancer
 - Age 45 or older with a first-degree relative (father or brother) diagnosed with prostate cancer at an early age (younger than age 65).
 - Age 40 or older with more than one first-degree relative who had prostate cancer at an early age (younger than age 65)
- Participation in an IND trial in the 30 days before randomization

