10.1.6 SAFETY OVERSIGHT

Safety oversight will be under the direction of a Data and Safety Monitoring Board (DSMB) composed of individuals with the appropriate expertise, including gastroenterology, hepatology, cardiology and statistics. Members of the DSMB are independent from the study conduct and free of conflict of interest, or measures should be in place to minimize perceived conflict of interest.

An Independent Medical Monitor and an independent Data and Safety Monitoring Board (DSMB), appointed by the NIDDK, will review the protocol for the VEDS trial and monitor the safety data as the trial progresses to ensure patient safety and to review efficacy. The DSMB is a multidisciplinary group with a written charge provided by the NIDDK. The DSMB reports to the NIDDK, which will communicate DSMB recommendations to the investigators, as appropriate. The DSMB will hold a meeting to approve the protocol. The DSMB will review performance and safety data. The DSMB may request more frequent meetings if necessary to fulfill its charge. It may also request additional safety reports on a more frequent basis. For example, all serious adverse events are reported to the DSMB for their consideration and recommendations as they occur.

Interim data on safety measures requested by the DSMB are reviewed at each of the scheduled semi-annual full meetings. Serious adverse events will be reviewed by the DSMB as they occur with the option of a teleconference discussion if any DSMB member so requests.

The DSMB will review quarterly reports by masked treatment groups of incident hepatotoxicities, as well as counts of patients who required more frequent liver function testing due to rises in ALT levels of more than 2 times baseline ALT or beyond 300 U/L. The DSMB will also examine the trends in ALT or AST levels for each patient who experiences a rise in ALT.

The DSMB also reviews the overall progress of the trial in terms of recruitment and data quality and makes a formal recommendation to the NIDDK at the end of each scheduled meeting as to whether the trial should continue unmodified, continue with protocol modifications, or be stopped.

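### The permanent-stop limit of 300 U/L lies inside the eligible ALT range and, for baselines above 100 U/L, below Grade 1 of the plan's own table; the passages need reconciling

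*Combined protocol and SAP*

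**What the plan says.** **Eligibility.** Section 5.1 requires ALT of at least 60 U/L. Section 5.2 excludes "Serum alanine aminotransferase (ALT) greater than 400 U/L within 90 days of randomization". Entry values from 60 to 400 U/L are therefore eligible.

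**Grading table (7.1).** The lowest ALT grade, Grade 1, is "BSL elevated: 3x BSL or >400 U/L". Grade 2 is more than 3 and up to 5 times baseline. At Grade 2 or higher the participant "will have the study medication stopped pending further study investigator evaluation", which is a hold.

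**Stop list (7.1).** This list is introduced as additional to the table, and any one item is enough. For an elevated baseline AST or ALT, drug is stopped in any of three cases:
- ALT or AST above 3 times baseline "or 300 U/L in two repeat tests (within 14 days");
- a value above 5 times baseline or above 500 U/L;
- a value above 3 times baseline or above 300 U/L ("whichever occurs first) AND total bilirubin" above 2 times ULN OR symptoms suggesting liver injury).

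The sentence after the list reads: "Follow-up visits will continue, but the study medication will not be restarted". The participant remains in the intention-to-treat analyses.

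**Related passages.** Section 6.3 defines hepatotoxicity by the drug-induced liver injury criteria of 7.1, without saying whether the table or the list is meant. Section 10.1.6 has the DSMB review counts of patients needing more frequent liver testing because of "rises in ALT levels of more than 2 times baseline ALT or beyond 300 U/L".

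**The concern.** The 400 U/L in the grading table matches the eligibility limit; the 300 U/L in the stop list does not. In the band between them, one stable ALT value is acceptable for entry, ungraded in the table, and grounds for permanently ending treatment once repeated. The order of the two actions also looks reversed: for many baselines the irreversible one is reached at a lower ALT than the hold.

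Two wording gaps add to this. The third item mixes AND with OR without brackets. Section 6.3 leaves open which set of criteria defines the hepatotoxicity outcome.

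Three things are at stake:
- whether sites apply an irreversible rule in the same way;
- whether some participants lose treatment because of their entry value rather than a new injury;
- whether hepatotoxicity counts can be interpreted. The trigger is also the primary endpoint variable, so a drug that lowers ALT makes the trigger less likely.

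**Working it through.** The plan gives no forecast of stops and no baseline ALT distribution, so there is no stated figure to reproduce.

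**1. Order of the limits.** For baseline B, compare 300 U/L with Grade 1 (taken as the lower of 3B and 400 U/L) and with the Grade 2 hold (above 3B).

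| B (U/L) | 300/B | Grade 1 from (U/L) | Hold above 3B (U/L) |
|---|---|---|---|
| 100 | 3.00 | 300 | 300 |
| 150 | 2.00 | 400 | 450 |
| 200 | 1.50 | 400 | 600 |
| 300 | 1.00 | 400 | 900 |
| 350 | 0.86 | 400 | 1050 |
| 400 | 0.75 | 400 | 1200 |

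300 < 3B whenever B > 100. Above that baseline the 300 U/L limit comes before both Grade 1 and the hold. At B = 150, a repeated value just over 300 U/L is ungraded yet stops drug permanently, whereas the hold needs more than 450 U/L.

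**2. Stable or improving participants.** The fall needed to reach 300 U/L is 1 - 300/B. At B = 350 it is 50/350 = 14.3%; at B = 400 it is 100/400 = 25%. Smaller improvements leave the participant above the limit.

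**3. The third item.** Let A be the ALT/AST limit, C bilirubin and S symptoms.
- Read as (A and C) or S, symptoms alone stop drug.
- Read as A and (C or S), symptoms count only with A. A participant who entered above 300 U/L and remains there then needs only a listed symptom, with no repeat test. Nausea is one of the listed symptoms, and section 2.3.1 also lists it as a possible effect of vitamin E.

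**4. Expected direction by arm.** Inputs from section 9.2: mean relative fall 20% on placebo and 40% on 800 IU, with SD 31% used as the between-participant SD. Assumptions: normality, the same SD at every baseline, and the week-24 means.

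P(ALT > 300 | B) = Φ((100(1 - 300/B) - mean fall)/31).

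At B = 350:
- placebo: Φ((14.3 - 20)/31) = Φ(-0.18) = 0.43;
- 800 IU: Φ((14.3 - 40)/31) = Φ(-0.83) = 0.20.

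| B (U/L) | Placebo | 800 IU |
|---|---|---|
| 150 | 0.0% | 0.0% |
| 200 | 1.2% | 0.2% |
| 250 | 9.8% | 2.6% |
| 300 | 25.9% | 9.8% |
| 350 | 42.7% | 20.3% |
| 400 | 56.4% | 31.4% |

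If both of two tests must exceed 300 U/L at B = 350, with an assumed correlation of 0.7 to 0.9, the figures are 30-36% on placebo and 12-15% on 800 IU.

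**5. Participants per arm.** Averaged over baselines assumed uniform on 300-400 U/L, the single-test probabilities are 42.2% and 20.4%. With an assumed share f of each arm of 50 in that band, the expected number is 50 × f × probability.

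| f | Placebo | 800 IU | Difference |
|---|---|---|---|
| 1% | 0.2 | 0.1 | 0.1 |
| 5% | 1.1 | 0.5 | 0.5 |
| 10% | 2.1 | 1.0 | 1.1 |
| 15% | 3.2 | 1.5 | 1.6 |

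Differences are taken before rounding. For one occasion these exceed the number of two-test confirmations. They do not bound the total over four treatment visits, nor stops under the third item.

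**The case against.** Several stronger readings are tempting, and the documents do not support them.

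- *Some participants meet a stopping criterion at entry.* No item is met by an entry ALT of 301-400 U/L alone. The first needs repeat testing within 14 days, the second more than 500 U/L or 5 times baseline, and the third bilirubin or symptoms. Scheduled treatment visits are at weeks 4, 8, 12 and 24, so the first item would ordinarily need an extra draw.
- *Sites cannot comply with all passages.* They can. The list adds to the table, and a site can act on whichever criterion is met. An absolute cap that binds before the multiple is also how the second and third items are expressly built. What remains is that nothing explains why the irreversible action can come at the lower value.
- *The DSMB count would include these participants from the first visit.* Section 10.1.6 speaks of rises that led to more frequent testing. A stable 350 U/L is not plainly a rise, so the text is unclear on this rather than wrong.
- *Stops will differ by arm and distort the result.* The direction follows from the plan's effect sizes, but the size rests on an undocumented share that could be close to zero. At a baseline of 150 U/L the calculated probability is essentially nil in both arms. Week-24 ALT is still collected after a stop, and an excess of stops on placebo removes no vitamin E.

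These objections limit the consequence. They do not remove the mismatch between 400 and 300 U/L, the missing exemption, the ungrouped AND/OR, or the open reference in section 6.3.

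**Conclusion.** The conflict stands on the wording alone. A stable or modestly improved participant who entered at 301-400 U/L would be permanently stopped once the value is repeated, while below Grade 1. For any baseline above 100 U/L the permanent stop can come before the hold. The third item and the hepatotoxicity definition each allow two readings.

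Stops would be expected to be somewhat more frequent on placebo, at about twice the 800 IU probability for a single test in the 300-400 U/L band. The difference of 0.1 to 1.6 participants per arm of 50 depends on the assumed 1-15% share, uniform baselines within the band, normality, a common SD and week-24 effects. The issue concerns exposure and hepatotoxicity counts; it is not a major threat to the primary result. It should be fixed because the rule is irreversible and the passages disagree, not because a large bias has been shown.

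**What to change.** The sponsor's clinicians and medical monitor should reconcile sections 5.2, 6.3 and 7.1 so that:

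- eligibility and the stop list agree on how an unchanged, eligible ALT above 300 U/L is handled;
- the hold and the permanent stop are placed in a consistent order across baselines;
- the AND/OR grouping in the third item is explicit;
- section 6.3 names the table or the list as the definition of hepatotoxicity.

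Section 10.1.6 should say whether stable entry values above 300 U/L count. Which values and actions to use is their clinical decision; none is proposed here.

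The cost is a protocol amendment to these passages and any matching data-system alert. No visits or tests are added.
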